#### **8.5.4.2 Microbiological Response Measures**

The number and percentage of subjects determined to have a by-subject microbiological response of success (eradication or presumed eradication), failure (persistence or presumed persistence) or indeterminate at the EOT, TOC and LFU Visits will be tabulated by treatment group for subjects in the microITT, microITT-2 (TOC Visit only) and ME-EOT (EOT Visit), ME-TOC (TOC Visit) and ME-LFU (LFU Visit) Analysis Sets. A 2-sided unadjusted 95% CI

for the difference in by-subject microbiological response success rates between the lefamulin and moxifloxacin treatment groups will be provided.

The proportion of subjects with a microbiological response of success by baseline pathogen (and where relevant, the susceptibility phenotype) at the TOC Visit will be tabulated separately by treatment group for subjects in the microITT-2 Analysis Set. The proportion of subjects with a microbiological response of success by baseline pathogen (and where relevant, the susceptibility phenotype) at the EOT Visit will be tabulated separately by treatment group for subjects in the microITT and ME-EOT Analysis Sets. The proportion of subjects with a microbiological response of sustained success by baseline pathogen (and where relevant, the susceptibility phenotype) at the LFU Visit will be tabulated separately by treatment group for subjects in the microITT and ME-LFU Analysis Sets.

A by-subject listing will present the by-pathogen and by-subject microbiological response at the EOT, TOC and LFU Visits in the ITT Analysis Set. A second by-subject listing will present the by-pathogen and by-subject microbiological response at the EOT, TOC and LFU Visits for non-responders, clinical failures, or subjects with persistence.

The proportion of subjects with a microbiological response of success at the TOC Visit by baseline pathogen (and where relevant, the susceptibility phenotype) and MIC to study drug received and by baseline pathogen (and where relevant, the susceptibility phenotype) and disk diffusion zone diameter will be determined for each pathogen isolated at baseline in the microITT and ME-TOC Analysis Sets.

A by-subject listing of subjects in the ITT Analysis Set with a superinfection or colonization will be provided. The listing will include subject ID, treatment group, baseline and post-baseline pathogen genus and species, study day of post-baseline pathogen, and whether the emergent pathogen is a superinfection or a colonization.

A by-subject listing of subjects in the ITT Analysis Set showing at least 1 pathogen with decreasing susceptibility will be presented in a listing providing the subject ID, treatment group, collection date/time and study day, type of specimen, pathogen (baseline and post-baseline), MIC values, disk diffusion zone diameters, and susceptibility to study drug received.

## **8.6 Pharmacokinetic Analyses**

Measured plasma concentrations of BC-3781 and BC-8041 will be summarized descriptively for the lefamulin group and nominal time point of collection. Summary statistics in the tabulation will include n, mean, standard deviation, CV [%], median, minimum and maximum.

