# 5.4 Study Drug Treatment

The duration of blinded study drug administration will be 7 days.

Subjects randomized to lefamulin will receive oral lefamulin 600 mg q12h for 5 days (10 doses) and oral moxifloxacin placebo q24h for 7 days (7 doses). Subjects randomized to moxifloxacin will receive oral moxifloxacin 400 mg q24h for 7 days (7 doses) and oral lefamulin placebo q12h for 5 days (10 doses).

On Day 1, study personnel will administer the first dose of study drug at the study site to all subjects, as soon as possible after the diagnosis of CABP and completion of all required Day 1 procedures as outlined in Table 1. While subjects are hospitalized, all doses of study drug will be administered by hospital staff or study personnel.

For Outpatients, or in the event a subject is discharged from the hospital during the study drug administration period, an adequate supply of study drug will be dispensed for self-administration at home. Subjects will be provided instructions regarding the dosing schedule. Subjects may self-administer oral study drug at home with the following exception: Study personnel will advise subjects who are Outpatients that they must return to the study site to assess CABP signs and symptoms at  $96 \pm 24$  hours after the first dose of study drug (see Section 6.11). Study personnel will inform Outpatients as to the timing of

this required study site visit. Subjects will be advised not to take their first dose of study drug at home that day, rather to bring their blister packs (used and unused) to the study site where they will take their dose while supervised, so that specific assessments can be performed both prior to and after taking the dose (see Sections 6.4 [ECGs] and 6.14 [PK]).

On Study Day 1, if q12h dosing is not feasible, the 1st and 2nd doses may be administered as close as 8 hours apart, in order to allow 2 doses to be given on Day 1. In this circumstance, the subject's dosing schedule should be adjusted on Day 2 to a regular q12h morning and evening schedule. Subsequently, every effort should be made to maintain a q12h dosing schedule. When this is not possible, it is acceptable to administer doses within 4 hours of the scheduled dosing time (i.e., a minimum of 8 hours between doses).

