#### 9.9 Pharmacokinetic Analyses

Measured plasma concentrations of lefamulin and its main metabolite, BC-8041, will be summarized descriptively by the actual time point of collection. Summary statistics in the

tabulation will include n, mean, standard deviation, CV [%], median, minimum and maximum.

Population PK modeling will be used to determine the individual model-predicted concentrations of lefamulin. Simulation of model output will enable descriptive statistical analysis of PK variables such as the  $C_{max}$ ,  $C_{min}$  and AUC for lefamulin.

A description of the population PK analysis will be described in a separate SAP. Results of this analysis will be reported separately.

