### 8.4.3 Study Drug Treatment Compliance

Each subject's compliance with study drug treatment will be calculated based on the number of doses the subject would have been expected to receive based on the number of treatment days (ie, the date of the first and last dose of study drug). Treatment compliance is defined as the number of doses actually received divided by the number of doses expected for the time period between the dates of the first and last doses of study drug ( $\times 100$ ). Subjects are expected to receive 7 days of study drug (5 days of active lefamulin plus 2 days of placebo) or moxifloxacin (7 days of active moxifloxacin). Descriptive statistics (number of subjects, mean, standard deviation, minimum, median, and maximum) will be presented for the ITT, microITT, CE-EOT and CE-TOC Analysis Sets.

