### 8.7.3 ECG Parameters

ECG data are being read centrally. The mean of the triplicates (or if triplicates not available, the duplicates or single ECG, whichever is available) will be used for all analyses, even if not performed within a 5-minute interval. Descriptive statistics for heart rate, PR interval, QRS interval, QT interval, and QT interval corrected by the Fridericia formula (QTcF) and the change from baseline at Day 1 (1-3 hours after the first dose of study drug), Day 4 (inpatients)/96±24h after the first dose of study drug (outpatients) (prior to the first dose of study drug) and Day 4 (1-3 hours after the first dose of study drug) will be summarized by treatment group for subjects in the Safety Analysis Set. In addition, Day 4 post-active dose will be summarized. Change from baseline will be calculated for each subject at Day 1 (1-3 hours after the first dose of study drug) and Day 4 (inpatients)/96±24h after the first dose of study drug (outpatients) (prior to and 1-3 hours after the first dose of study drug) as the value at the specified visit and time point minus the baseline value. The change from baseline to the minimum and maximum post-baseline values will also be summarized by treatment group, where these post-baseline values include unscheduled visits. Change from baseline will be calculated for each subject as the minimum or maximum post-baseline value minus the baseline value. Baseline is defined as the mean of the triplicates from the last assessment prior to the first dose of study drug. ECG parameters for each of the triplicates (including the change in QTcF value from pre-dose to post-dose) and the overall interpretation of the ECG will be presented on a listing.

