### ECG:

Analysis Visit and Timepoint	Timepoint	Target Day	If scheduled study visit assessment not available:	
			Consider Unscheduled assessment for Analysis Visit?	Study Days acceptable for Analysis Visit
Baseline	Screening or Day 1 pre-dose or Unscheduled 		Yes	-4 to ≤1 ( pre-dose )
Day 1 post dose	Day 1 post-dose	1	No	-
Day 4 pre dose	Day 4  pre-dose	4	No	-
Day 4 post dose 	Day 4  post-dose	4	No	-
Unscheduled 	Unscheduled	-	-	-

Notes: N/A: Not applicable.

 Baseline is the mean of the triplicates (or duplicates or single if a triplicate is not obtained) from the last assessment prior to the first dose of study drug.

The timepoint identified as the Day 4 or 96 +/- 24 hour timepoint regardless of visit.

 Any unscheduled assessments (i.e., timepoint="Unscheduled") not meeting the criteria for an analysis visit.

 In addition, Day 4 post-active dose will be summarized.

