**Safety Laboratory:**

Analysis Visit	Study Visit	Target Day	If scheduled study visit assessment not available:		
			Consider Unscheduled central assessment for Analysis Visit? 	Consider Local lab assessments for Analysis Visit?	Study Days acceptable for Analysis Visit
Baseline	Screening 	-	Yes	No	-4 to ≤1 
Day 4	Day 4 	4	Yes	No 	3 to 6
EOT 	EOT	-	Yes	No 	within 2 days after the last dose of study drug (i.e., last day of study drug through 2 subsequent calendar days)
TOC	TOC	-	Yes	No 	5-10 days after last dose of study drug
LFU	LFU	30	Yes	No 	27 to 33
Unscheduled 	-	-	Yes	Yes 	-

Notes: EOT: End of Treatment; TOC: Test of Cure; LFU: Late Follow-up; N/A: Not applicable.

 Except for Baseline, if more than 1 central measurement is taken during the visit window (and no scheduled is taken) the earliest value will be analyzed.

 Provided the date and time of collection is on or before the date and time of first dose

 The visit identified as the 96 +/- 24 hour visit (i.e., study visit Day 4, Day 5, or Day 6).

 Local labs assessment are to be included in the identification of worst post-baseline values (i.e. minimum, maximum, highest, lowest, any post-baseline, and PCS). See section 8.7.2.

 If an EOT assessment is done within the day 4 visit window, and no assessment was done at the study day 4 visit, the assessment will be reported at both the Day 4 and EOT analysis visits.

 Any unscheduled assessments not meeting the criteria for an analysis visit.

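### SAP 8.6 can tabulate outpatient Day 6 samples taken after placebo as post-dose lefamulin levels, and the Day 4 post-active-dose QTcF summary is undefined

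*SAP*

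**What the plan says.** **Dosing.** Under Protocol 5.4 the lefamulin arm takes "oral lefamulin 600 mg q12h for 5 days (10 doses) and oral moxifloxacin placebo q24h for 7 days (7 doses". SAP 8.4.3 describes the same course as "5 days of active lefamulin plus 2 days of placebo". The moxifloxacin arm is on active drug for all 7 days. Two lefamulin-type doses are intended on Day 1, as little as 8 h apart if needed.

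**Visit.** Protocol 6.1.1 places the outpatient visit 72 to 120 h after the first dose. SAP Appendix D, in its safety laboratory table, describes this visit as "The visit identified as the 96 +/- 24 hour visit (i.e., study visit Day 4, Day 5, or Day 6".

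**Sampling.** Protocol 6.14 and Table 5 time the PK samples before, and 1–2, 3–4 and 8–9 h after, the first study-drug dose of that day. Nothing requires that dose to be lefamulin. Inpatient sampling is limited to Day 4 or Day 5. Protocol 6.4 ties the ECGs to the day's first dose in the same way.

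**Analysis.** SAP 8.6 uses nominal time: "Measured plasma concentrations of BC-3781 and BC-8041 will be summarized descriptively for the lefamulin group and nominal time point of collection". Protocol 9.9 says that concentrations "will be summarized descriptively by the actual time point of collection". SAP 9.0, which lists departures from the protocol, does not mention the difference. For ECGs, Appendix D takes as Day 4 "The timepoint identified as the Day 4 or 96 +/- 24 hour timepoint regardless of visit". SAP 8.7.3 then adds: "In addition, Day 4 post-active dose will be summarized".

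**The concern.** The two arms stop active treatment on different days, but sampling is tied to the generic study-drug dose. On Day 6 that dose can be a placebo capsule for a lefamulin subject. Under a nominal-time rule with no active-dose condition, the resulting concentrations go into the same rows as samples taken shortly after a lefamulin tablet. Those rows would show lower means and a larger coefficient of variation for lefamulin and BC-8041. This table is the only PK output that the SAP covers (SAP 1.0).

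The ECG has a related weakness. Protocol 1.5.3 describes lefamulin's QT effect as dependent on peak concentration. A Day 4 post-dose comparison that takes every ECG from this visit can set lefamulin after placebo against moxifloxacin after active drug. The SAP recognises this by adding a post-active-dose summary, but it neither defines that summary nor says which one carries the between-arm comparison.

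**Working it through.** **Inputs.** Visit window 96 ± 24 h (Protocol 6.1.1); ten lefamulin doses, q12h, over 5 days, with a minimum 8 h gap on Day 1 (Protocol 5.4); PK sample times (Protocol Table 5); half-life 8.6–11.8 h, from IV data (Protocol 1.5.1). Assumed: dosing at 08:00 and 20:00 from Day 2, and site hours of 08:00–17:00.

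**1. The plan's own figures.** 96 − 24 = 72 h and 96 + 24 = 120 h. 5 days × 2 = 10 doses. On a strict 12 h schedule, dose 10 falls at 9 × 12 = 108 h. The window therefore stays open for 120 − 108 = 12 h after the last lefamulin dose.

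**2. A permitted example.** First dose at 14:00 on Day 1, second at 22:00, then 08:00 and 20:00. The count is 2 + (2 × 4) = 10, with the last dose at 20:00 on Day 5, which is 102 h. An 08:00 visit falls at:

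| Visit day | Hours after first dose | In window? | Lefamulin-arm dose at visit |
|---|---|---|---|
| 4 | 66 | no | active |
| 5 | 90 | yes | active |
| 6 | 114 | yes | placebo only |

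**3. What the labels mean on Day 6.** The visit is 12 h after the last lefamulin dose, so true time = nominal time + 12 h. Remaining concentration relative to the 12 h trough is 2^(−t/half-life), with t the nominal time:

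| Nominal label | True time since lefamulin | Share of 12 h trough |
|---|---|---|
| pre-dose | about 12 h | 100% (a genuine trough) |
| 1–2 h | 13–14 h | 85–94% |
| 3–4 h | 15–16 h | 72–84% |
| 8–9 h | 20–21 h | 48–63% |

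The last column assumes that the IV half-life applies. The direction does not depend on that: the three post-dose rows contain declining levels with no new peak.

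**4. How often.** The documents give no figure. If visits were spread evenly over in-window site hours, a first dose at clock hour h leaves 17 − h hours on Day 4, 9 on Day 5 and h − 8 on Day 6, a total of 18. The Day 6 share is (h − 8)/18:
- 08:00: 0/18 = 0%
- 12:00: 4/18 = 22%
- 14:00: 6/18 = 33%
- 16:00: 8/18 = 44%

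After 16:00, two doses 8 h apart no longer fit on Day 1. The count by the end of Day 5 is then 1 + (2 × 4) = 9, and the Day 6 morning dose can be active lefamulin. The even spread is illustrative; the 96 h target itself falls on Day 5.

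**5. Nominal against actual time.** Protocol 9.9 says actual time but does not say actual time since what. Table 5 counts from the first study-drug dose of the day. Counted that way, a Day 6 sample would still read 1–2 h. The SAP–protocol discrepancy and the missing active-dose condition are therefore separate defects, and curing the first does not cure the second.

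**The case against.** The strongest reply is that little of consequence rests on the affected table. Cmax, Cmin and AUC come from population PK modelling, reported separately, and Protocol 6.14 calls for exact dosing and sampling times for that purpose. A reader might infer that the trial will understate lefamulin exposure. The documents do not support this, because the exposure estimates do not use the SAP 8.6 labels.

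A reader might also infer that the QTcF results will flatter lefamulin. That goes too far. SAP 8.7.3 plans the post-active-dose summary and a Day 1 summary 1–3 h after the first dose in both arms, and the any-post-baseline QTcF categories include the Day 1 ECGs. What remains is that the unrestricted Day 4 post-dose summary can be asymmetric, and the restricted one has no definition. A restricted summary also cannot supply an on-drug ECG for a subject first seen on Day 6; it can only leave that subject out.

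A third tempting step is to apply the half-life over 12 h, 2^(−12/8.6) = 38% to 2^(−12/11.8) = 49%, as a ceiling on a Day 6 value relative to a correctly labelled one. It is not a valid ceiling. Protocol 1.5.1 describes two oral absorption peaks, the second at 1–4 h, so a 1–2 h sample may precede the higher level.

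Finally, the Day 6 wording in Appendix D belongs to the laboratory table and is not a PK rule. That is true, but the 120 h limit reaches Day 6 without it. The objection narrows the point and does not remove it.

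**Conclusion.** The point holds in a limited form. SAP 8.6 would place some post-placebo samples in post-dose lefamulin rows, and it departs from Protocol 9.9 without listing the change. The effect is lower post-dose means and an inflated CV in one descriptive table. It touches only lefamulin-arm outpatients seen on Day 6 after all ten doses. Their number is unknown; the 0–44% range rests on assumed site hours and evenly spread visits. Day 6 pre-dose troughs, population PK and the efficacy analyses are unaffected.

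For QTcF, the safeguard exists but is not specified well enough to be programmed unambiguously or to show which summary is the between-arm comparison.

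**What to change.** 1. **SAP 8.6 and 9.0.** Reconcile with Protocol 9.9 and list any remaining change. Summarise concentrations by actual time since the last active lefamulin dose, using the recorded dosing and sampling times. Show post-dose samples not preceded by an active lefamulin dose that day separately, outside the post-dose rows. Keep Day 6 pre-dose samples as troughs.
2. **SAP 8.7.3 and Appendix D.** Define post-active dose as an ECG 1–3 h after an active dose of the assigned drug. Use that summary for the between-arm Day 4 post-dose QTcF comparison. Keep the any-post-baseline QTcF category tables for all subjects, so that no safety data are dropped.

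**Cost.** SAP wording and programming only, with no new data. Somewhat fewer subjects will appear in the Day 4 post-dose rows.

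I would not restrict the visit days. The same visit supplies the in-person symptom assessment for the primary ECR endpoint, and SAP 6.1 falls back on telephone data when that is missing.

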## **8.7 Safety Analyses**

All safety analyses will be conducted in the Safety Analysis Set. Subjects who receive the wrong study drug for their entire course of treatment will be analyzed in the group based on the drug received. Subjects who receive the wrong study drug less than the entire course of treatment will be analyzed in the as randomized treatment group.

For each safety parameter with the exception of ECGs which are measured in triplicate at each time point and vital signs which uses the last assessment prior to Day 1, the last assessment made prior to the first dose of study drug will be used as the baseline for all analyses.

### **8.7.1 Adverse Events**

Adverse events will be monitored throughout the study from the time a subject is consented through the TOC Visit; SAEs are to be collected from the time of consent through the LFU Visit. Adverse events will be coded using Version 18.0 or higher of MedDRA. A treatment-emergent AE (TEAE) is defined as an AE that starts or worsens at or during the time of or after the first study drug administration. If the AE start date is unknown or is a partial date such that it cannot be determined if the AE started on or after the first study drug administration, it will be categorized as a TEAE.

An overall summary of AEs will include the number and percentage of subjects who experienced at least 1 AE of the following categories: any AE, any TEAE, any serious TEAE, any treatment-related TEAE, any treatment-related serious TEAE, any TEAE leading to premature discontinuation of study drug, any TEAE leading to premature discontinuation from the study, and any TEAE leading to death.

The number and percentage of subjects reporting a TEAE and the number and percentage of subjects reporting a treatment-related TEAE (related defined as possibly, probably or definitely related to study drug) in each treatment group will be tabulated by system organ class, preferred term, and severity (mild, moderate, and severe). A summary of TEAEs and treatment-related TEAEs sorted by decreasing frequency of preferred term in lefamulin subjects will also be provided. Likewise, the number and percentage of subjects reporting a serious TEAE and the number and percentage of subjects reporting a TEAE leading to premature discontinuation of study drug in each treatment group will be tabulated separately by system organ class and preferred term. For all analyses of TEAEs, if the same AE (based on preferred term) is reported for the same subject more than once, the AE is counted only once for that preferred term and at the highest severity and strongest relationship to study drug.

A listing of TEAEs leading to discontinuation of study drug will be provided and will include subject ID, subject age, sex and race, onset day of the AE, duration of AE in days, duration of study drug (days), preferred term, verbatim term, severity, relationship to study drug, outcome, therapy given (Y/N) and seriousness (Y/N). A listing of all serious TEAEs will also be provided and will include subject ID, subject age, sex and race, onset day of the AE, duration of AE in days, preferred term, verbatim term, severity, relationship to study drug, outcome, therapy given (Y/N) and drug withdrawn (Y/N). If the outcome of the SAE is death, the date and study day of the death and whether it was prior to EOT or after EOT will be presented.

### **8.7.2 Clinical Laboratory Evaluations**

Central laboratory data will be utilized for all analyses. For the purposes of summarizing post-baseline maximum alkaline phosphatase (ALP), alanine aminotransferase (ALT), aspartate aminotransferase (AST), and total bilirubin and for the purposes of identifying cases of potential Hy's law, both central and local laboratory data will be used. In addition, local laboratory data

will be utilized in the assessment of any Potentially Clinically Significant (PCS) labs as defined in [Appendix B](#). Local laboratory data are collected on the eCRF: 1) if the subject did not meet the laboratory inclusion/exclusion criteria based on the central laboratory results, 2) potential Hy's law is reported based on local laboratory results, and 3) the Principal Investigator chooses to report local laboratory results obtained in the clinical management of the patient.

Laboratory values will be defined as potentially clinically significant (PCS) according to the table in [Appendix B](#). To be considered PCS, the laboratory value must meet both the lower limit and the percent decrease from baseline or both the upper limit and the percent increase from baseline. The proportion of subjects in the Safety Analysis Set with at least 1 PCS laboratory value will be summarized by treatment group and PCS laboratory values will be summarized by treatment group, laboratory parameter, visit and for the overall worst post-baseline value (minimum and maximum value, where appropriate defined in [Appendix C](#)). Percentages for each laboratory test will be based on the number of subjects with a baseline and post-baseline evaluation at the visit for the specific laboratory test. By-subject listings of all laboratory values for a subject with any PCS post-baseline laboratory value will also be provided.

Shift tables will be presented to show the number and percentage of subjects with a laboratory value below the lower limit of normal (LLN), within normal limits, above the upper limit of normal (ULN) and missing at baseline versus the value at each visit and the worst post-baseline value. Percentages for each laboratory test will be based on the number of subjects in the Safety Analysis Set.

A listing of subjects who have the laboratory criteria for potentially meeting Hy's Law will also be provided. The laboratory criteria for potentially meeting Hy's Law is defined as ALT or AST  $>3 \times \text{ULN}$ , ALP  $\leq 2.0 \times \text{ULN}$  and total bilirubin  $>2 \times \text{ULN}$ . The proportion of subjects with any post-baseline AST  $>3 \times \text{ULN}$ ,  $>5 \times \text{ULN}$  and  $>10 \times \text{ULN}$ , any post-baseline ALT  $>3 \times \text{ULN}$ ,  $>5 \times \text{ULN}$  and  $>10 \times \text{ULN}$ , any post-baseline total bilirubin  $>1.5 \times \text{ULN}$  and  $>2 \times \text{ULN}$ , any post-baseline ALP  $>2 \times \text{ULN}$ , and any post-baseline ALT or AST value  $>3 \times \text{ULN}$  and any post-baseline total bilirubin value  $>2 \times \text{ULN}$  with an ALP  $\leq 2 \times \text{ULN}$  and with an ALP  $>2 \times \text{ULN}$  will be presented by treatment group.

Descriptive statistics for chemistry and hematology parameter values and the change from baseline at Day 4, EOT, and TOC will be summarized by treatment group for the Safety Analysis Set. Change from baseline will be calculated for each subject at the specified visit as the value at the specified visit minus the baseline value. The change from baseline to the minimum and maximum post-baseline values for chemistry and hematology parameters will also be summarized by treatment group. Change from baseline will be calculated for each subject as the minimum or maximum post-baseline value minus the baseline value. Baseline is defined as the last assessment prior to the first dose of study drug. Box-plots, which provide the median, mean, inter-quartile range, 5th and 95th percentile, and outliers will also be provided for ALP, AST, ALT, BUN, calcium, creatinine, phosphate, sodium, total bilirubin, absolute neutrophil count, hemoglobin, platelets, and WBC by scheduled study visit and treatment group.

Urinalysis data will be provided in a listing.

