**APPENDIX B: CLINICAL LABORATORY POTENTIALLY CLINICALLY SIGNIFICANT VALUES**

Parameter	Lower Limit	% Decrease from Baseline	Upper Limit	% Increase from Baseline
HEMATOLOGY				
Hemoglobin	<0.8 x LLN	>20%	>1.3 x ULN	>30%
WBC	<0.65 x LLN	>60%	>1.6 x ULN	>100%
Neutrophils	<0.65 x LLN	>75%	>1.6 x ULN	>100%
Lymphocytes	<0.65 x LLN	>75%	>1.6 x ULN	>100%
Platelets	<0.65 x LLN	>50%	>1.5 x ULN	>100%
CHEMISTRY				
Sodium	<0.85 x LLN	>10%	>1.1x ULN	>10%
Potassium	<0.8 x LLN	>20%	>1.2xULN	>20%
Creatinine	NA	NA	>2.0 x ULN	>100%
Urea nitrogen (BUN)	NA	NA	>3.0 x ULN	>200%
Calcium	<0.7 x LLN	>30%	>1.3 x ULN	>30%
Magnesium	<0.5 x LLN	>50%	NA	NA
Phosphorus	<0.5 x LLN	>50%	>3.0 x ULN	>200%
Alkaline phosphatase	<0.5 x LLN	>80%	>2.0 x ULN	>100%
ALT	NA	NA	>3.0 x ULN	>200%
AST	NA	NA	>3.0 x ULN	>200%
GGT	NA	NA	>3.0 x ULN	>200%
Total bilirubin	NA	NA	>=2.0 x ULN	>150%
Albumin	<0.5 x LLN	>50%	>1.5 x ULN	>50%
Glucose	<0.6 x LLN	>40%	>3.0 x ULN	>200%

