**APPENDIX C: DIRECTIONALITY OF WORST LABORATORY PARAMETERS**

Laboratory Test	Parameter	Worst Value
Hematology	Hematocrit	Lowest value
	Red blood cell count	Lowest value
	Mean cell hemoglobin	Lowest value
	Mean cell hemoglobin concentration	Lowest value
	Hemoglobin	Lowest value
	Mean cell volume	Lowest value
	White blood cell count	Lowest value
	Platelets	Lowest value
	Neutrophils	Lowest value
	Lymphocytes	Lowest value
	Monocytes	Lowest value
	Eosinophils	Highest value
	Basophils	Lowest value
Chemistry	Albumin	Lowest value
	Alkaline phosphatase	Highest value
	Alanine aminotransferase (ALT/SGPT)	Highest value
	Aspartate aminotransferase (AST/SGOT)	Highest value
	Blood urea nitrogen (BUN)	Highest value
	Calcium	Both highest value and lowest value
	Chloride	Both highest value and lowest value
	Creatinine	Highest value
	Creatine kinase (CK)	Highest value
	Direct bilirubin	Highest value
	Gamma-glutamyl transferase (GGT)	Highest value
	Glucose	Both highest value and lowest value
	Magnesium	Both highest value and lowest value
	Phosphorus	Both highest value and lowest value
	Potassium	Both highest value and lowest value
	Sodium	Both highest value and lowest value
	Total bilirubin	Highest value
	Total protein	Lowest value
	Uric acid	Highest value
Other Tests	Procalcitonin	Highest value

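### For seven laboratory limits Appendix C looks only at the opposite tail, so PCS events can be missed in the by-parameter overall worst summary

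*SAP*

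**What the plan says.** SAP Section 8.7.2 defines PCS in either direction: a value "must meet both the lower limit and the percent decrease from baseline or both the upper limit and the percent increase from baseline". The limits are in Appendix B ("CLINICAL LABORATORY POTENTIALLY CLINICALLY SIGNIFICANT VALUES").

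The same section then specifies these PCS outputs:

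- An overall proportion: "The proportion of subjects in the Safety Analysis Set with at least 1 PCS laboratory value will be summarized by treatment group".
- PCS values by arm, parameter and visit, and also "for the overall worst post-baseline value (minimum and maximum value, where appropriate defined in" Appendix C ("DIRECTIONALITY OF WORST LABORATORY PARAMETERS").
- "By-subject listings of all laboratory values for a subject with any PCS post-baseline laboratory value will also be provided".

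Separately: "The change from baseline to the minimum and maximum post-baseline values for chemistry and hematology parameters will also be summarized by treatment group".

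SAP Section 7.2.3 brings all scheduled and unscheduled assessments into the overall worst and PCS analyses. Appendix D (safety laboratory table, footnote 4) adds local-laboratory results to the worst post-baseline and PCS values, but does not let local results stand in for a scheduled analysis visit.

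**The concern.** Appendix B decides what counts as PCS, and Appendix C decides which post-baseline value is examined in the overall worst row. The two should agree in direction. For five two-sided parameters they do: sodium, potassium, calcium, phosphorus and glucose have limits on both sides, and Appendix C takes both extremes. For seven others Appendix B has two limits but Appendix C takes one extreme.

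The overall worst summary is the only output that is meant to give PCS incidence by parameter and by arm across every post-baseline value, including unscheduled and local draws. If it looks at the wrong end of a subject's values, it can undercount. Protocol Section 9.7 promises the number and percent of subjects with treatment-emergent PCS laboratory values and does not restrict the direction. A high WBC is also relevant in this trial: a worsening elevated WBC that leads to non-study antibacterial therapy is one of the criteria for an investigator-assessed failure (Protocol Section 6.12.1).

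**Working it through.** The plan states no figure to reproduce. The check sets the two appendices side by side.

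**Step 1. Count the limits in Appendix B.**

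- Hematology: 5 parameters × 2 limits = 10.
- Chemistry with two limits: sodium, potassium, calcium, phosphorus, alkaline phosphatase, albumin, glucose: 7 × 2 = 14.
- Chemistry with one limit: creatinine, BUN, magnesium, ALT, AST, GGT, total bilirubin: 7 × 1 = 7.
- Total: 10 + 14 + 7 = 31 limits on 19 parameters, of which 5 + 7 = 12 have limits on both sides.

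**Step 2. Compare directions for those 12 parameters.**

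| Parameter | Appendix B limits | Appendix C worst value | Limit not matched |
|---|---|---|---|
| Hemoglobin | low, high | lowest | high |
| WBC | low, high | lowest | high |
| Neutrophils | low, high | lowest | high |
| Lymphocytes | low, high | lowest | high |
| Platelets | low, high | lowest | high |
| Albumin | low, high | lowest | high |
| Alkaline phosphatase | low, high | highest | low |
| Sodium, potassium, calcium, phosphorus, glucose | low, high | both | none |

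Six upper limits plus one lower limit give 7 unmatched limits: 7/31 = 23%. The seven one-sided parameters are all matched. Magnesium has both directions in Appendix C but only a low limit in Appendix B, and that loses nothing.

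**Step 3. When is an event missed?** A value v is PCS-high if v > c × ULN and v > (1 + p) × baseline, where c is the multiple of ULN and p the proportional increase in Appendix B. Both conditions become easier to meet as v rises. So the lowest post-baseline value is PCS-high only if every post-baseline value is. A high event is therefore missed exactly when at least one post-baseline value is PCS-high and at least one is not. The same holds in mirror image for low alkaline phosphatase.

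Illustration for platelets, with assumed LLN 150, ULN 400 and baseline 300. PCS-high needs v > 1.5 × 400 = 600 and a rise above 100%, that is v > 2 × 300 = 600. PCS-low needs v < 0.65 × 150 = 97.5 and a fall above 50%, that is v < 150.

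| Post-baseline values | Any value PCS-high? | Lowest value | Lowest value PCS? | In the overall worst row? |
|---|---|---|---|---|
| 650, 350, 300 | yes | 300 | no | missed |
| 650 | yes | 650 | yes (high) | kept |
| 650, 700, 640 | yes | 640 | yes (high) | kept |

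Central laboratory draws are scheduled at Day 4, EOT and TOC (Appendix A). A subject with full follow-up has at least three post-baseline values, and a single one that is not PCS in that tail removes the event.

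**Step 4. Where else does a missed event show?**

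| Output | By arm | By parameter | Unscheduled and local values | PCS count |
|---|---|---|---|---|
| At least one PCS value | yes | no, as written | yes | yes |
| By-visit PCS | yes | yes | only unscheduled central values assigned to an analysis visit; no local values | yes |
| Listings | no counts | shown | yes | no |
| Change to minimum and maximum | yes | yes | unscheduled included | no |
| Overall worst PCS | yes | yes | yes | yes, but one-sided for the seven limits |

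No other row combines all four features.

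**The case against.** The case against is substantial and narrows the point. A reader might infer that these events can never appear in the overall worst table, which would then show zero for the seven limits whatever happens. The documents do not support that. Section 8.7.2 counts a value as PCS in either tail, so the lowest value is also tested against the upper limit, and Step 3 shows series in which the event is kept.

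A reader might also infer that a high WBC at an unscheduled draw disappears from the incidence tables altogether. That is not supported either. The proportion with at least one PCS value does not depend on Appendix C, and Section 7.2.3 and Appendix D bring unscheduled and local values into it. The listings show the event, and the change to minimum and maximum covers both directions for hematology and chemistry.

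It is fair to add that 7 of 31 counts table cells, not events. The high WBC and neutrophil limits also need a rise of more than 100% from baseline, in subjects who may enter with WBC above 10,000 cells/mm³ as a qualifying sign. The documents give no basis for estimating how often such events occur.

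What remains is the by-parameter gap. The at-least-one proportion, as written, does not say which test or which direction differs between arms. The listings give no incidence, and the change summaries give no PCS count.

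**Conclusion.** The mismatch is real, and its consequence is limited. For 7 of 31 PCS limits, events in the opposite tail can be missed in the by-parameter overall worst summary whenever the subject has another post-baseline value that is not PCS in that tail. Missed events at an analysis visit still appear by parameter and arm in the by-visit table. Missed events seen only at local draws, or at unscheduled draws not assigned to an analysis visit, have no by-parameter incidence by arm.

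This rests on two readings of the SAP. First, the at-least-one-PCS proportion is taken as one figure across all tests, since 8.7.2 names no parameter breakdown for it. Second, the Unscheduled category in Section 7.2.3 is taken to have no row of its own in the by-visit PCS table, since the SAP does not provide for one. The number of events affected cannot be estimated from the documents. This is a correction to a descriptive safety table, with no effect on efficacy conclusions, the non-inferiority test or sample size.

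**What to change.** Either of two changes closes the gap, taking unmatched limits from 7 of 31 to 0 of 31:

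1. In Appendix C, specify both the highest and the lowest value for hemoglobin, WBC, neutrophils, lymphocytes, platelets, albumin and alkaline phosphatase, as is already done for sodium, potassium, calcium, phosphorus and glucose.
2. In Section 8.7.2, state that the by-parameter overall PCS incidence counts any post-baseline value, whether scheduled, unscheduled or local, that meets either Appendix B limit with its change criterion. Section 8.7.4 already works this way for vital signs: Table 11 has high and low criteria, and the overall incidence includes unscheduled visits.

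The cost is seven table cells or one sentence, plus the matching programming. No data collection changes. It should be made in a SAP amendment before database lock.
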